#### **4.3.8 Thrombotic microangiopathy**

The proportion of participants experiencing thrombotic microangiopathy by 6 months post-randomization will be estimated and compared between treatment groups using the Z test for comparing binomial proportions (or Barnard's Exact Unconditional Test as appropriate).

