# TABLE 1. SIROLIMUS TOXICITIES

(L) Toxicity may also occur later.

Toxicities will be scored as per the NCI's Common Terminology Criteria for Adverse Events (CTCAE) version 4.0, unless otherwise specified.

• *Hyperlipidemia:* In the Phase III studies, treatment of new-onset hypercholesterolemia with lipid-lowering agents was required in 42-52% of patients enrolled in the sirolimus arms. Concomitant administration of sirolimus and HMG-CoA reductase inhibitors (statins) and/or fibrates appeared to be well tolerated. However, statins or fibrates should only be administered with caution to patients being treated with sirolimus and a CNI, at doses which are reduced according to label recommendations. Treated patients should be monitored for the development of rhabdomyolysis. Sirolimus should be continued during

therapy for hypercholesterolemia and hypertriglyceridemia unless the lipid levels are uncontrollable with standard therapy and are deemed to be at risk to the subject, per the treating physician.

• *Thrombotic Microangiopathy (TMA):* Studies in adult transplant patients have shown an increase in TMA from 4.2% when patients were treated with tacrolimus or cyclosporine alone compared to 10.8% in patients treated with the tacrolimus/sirolimus combination. TMA may occur both in the setting of sirolimus and/or CNI levels being above the therapeutic range or when levels are within desired ranges. Although complete renal recovery occurred in 92% of these patients, the potential seriousness of this complication requires careful monitoring and management.

To meet the definition (BMT CTN Consensus Definition) for TMA, a patient must have all of the following:

- 1. RBC fragmentation and  $\geq 2$  schistocytes per high-power field on peripheral smear
- 2. Concurrent increased serum LDH above institutional baseline
- 3. Concurrent renal\* and/or neurologic dysfunction without other explanations
- 4. Negative direct and indirect Coombs test results

\*Doubling of serum creatinine from baseline (baseline = creatinine before hydration and conditioning) or 50% decreased in creatinine clearance from baseline

BMT CTN Consensus for TMA severity scoring:

Grade I	Evidence of RBC destruction (schistocytosis) without clinical
	consequences
Grade II	Evidence of RBC destruction with increased creatinine $\leq 3 \times ULN$
Grade III	Evidence of RBC destruction with creatinine $> 3 \times ULN$ not requiring
	dialysis

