#### 7. Hyperlipidemia

Prevalence of hyperlipidemia as measured by fasting lipid panel and use of lipid-lowering agents at baseline, Days 28, 56 and 180 post-randomization will be compared between groups at each timepoint using a Z-test for binomial proportions (or Barnard's Exact Unconditional test as appropriate).

8. Post-transplant thrombotic microangiopathy

Cumulative incidence of post-transplant thrombotic microangiopathy will be estimated (treating death as a competing risk) and curves will be compared using Gray's test. Estimates and confidence intervals will be provided for 6 months post-randomization.

9. CMV-reactivation

Proportion of patients requiring therapy for CMV-reactivation by Day 56 post-randomization will be compared between treatment groups using a Z-test (or Barnard's Exact unconditional as appropriate).

10. Change in Patient-Reported Outcomes from Enrollment to Day 56, 6 months and 1 year. Participant self-reported measures will be assessed using the MDASI, FACT-BMT, and MOS SF-36 (or PedsQL for Pediatric patients) at enrollment, day 56, 6 months and 1 year. These will be scored according to the recommendations of the developers. Patient reported outcomes at each time point will be summarized using simple descriptive statistics (mean, SD). PRO among survivors at each time point will be compared between treatment arms in an initial analysis using two sample t-statistics. The missing data pattern of the PRO measurements will be examined using graphical techniques and logistic regression models conditional on survival. At each time point, estimates of the difference in PRO between the treatments conditional on survival at that

time point will be obtained using inverse probability of censoring weighting with independent estimating equations to account for missing data.

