## **2.2 Handling Missing Data**

Because the primary endpoint, aGVHD response at Day 28 post-randomization, is evaluable after a short time, we expect very little to no impact of missing data on its analysis. Furthermore, since all endpoints will be evaluable within 1 year of randomization, we do not expect missingness to affect their analyses appreciably. An Endpoint Review Committee will adjudicate data on the primary endpoint to resolve this endpoint for participants with missing data. Any remaining missing values which are not able to be adjudicated will be excluded from the analyses. If any participants have missing data on the primary endpoint, a sensitivity analysis that treats missing responses as failures for aGVHD response will be conducted to examine the robustness of analysis results.

Based on previous BMT CTN studies and other clinical research, it is expected that the data collected on patient reported outcomes will not be complete. Logistic models will be constructed to investigate whether specific patient, clinical, or other variables are predictive of this missingness. If this is the case, inverse probability weighting will be employed to adjust for covariate-dependent missingness in comparing patient reported outcomes between treatment groups.

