#### **4.3.4 EBV-associated lymphoproliferative disorder**

The cumulative incidence of EBV-associated lymphoproliferative disorder or EBV reactivation therapy will be described using the Aalen-Johansen estimator, treating death as the competing risk. Cumulative incidence curves will be compared between treatments using Gray's test.

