**Exhibit 1501-20: Thrombotic Microangiopathy**

Thrombotic Microangiopathy at 6 Months Post-randomization by Treatment Group			
	Sirolimus (N=) N (%)	Prednisone (N=) N (%)	P-value*
Yes	XX (XX.X%)	XX (XX.X%)	X.XXX
No	XX (XX.X%)	XX (XX.X%)	
Not Evaluable	XX	XX	

\* Clarify test used (Z test of binomial proportions or Barnard's Exact)

Clarify the population for the endpoint (n=?). If n is not the same as the primary endpoint, explain why (e.g. patient not evaluable, missing data, etc.)

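### The SAP replaces the protocol's cumulative incidence of TMA by a 6-month proportion, giving no reason, no confidence interval and no rule for who is not evaluable

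*SAP*

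**What the plan says.** Protocol 5.2.6 item 8: "Cumulative incidence of post-transplant thrombotic microangiopathy will be estimated (treating death as a competing risk) and curves will be compared using Gray's test". It also promises 6-month estimates with confidence intervals.

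SAP 4.3.8: "The proportion of participants experiencing thrombotic microangiopathy by 6 months post-randomization will be estimated and compared between treatment groups using the Z test", or Barnard's exact test where appropriate. It names no competing event, no censoring and no interval.

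SAP Exhibit 1501-20, titled "Thrombotic Microangiopathy at 6 Months Post-randomization by Treatment Group", has rows *Yes*, *No* and "Not Evaluable" and a p-value column. The third row shows a count without a percentage, so it appears to lie outside the denominator. The shell does not define it. If the n differs from that of the primary endpoint, the author is only asked to "explain why (e.g. patient not evaluable, missing data, etc".

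SAP 2.2 has one general sentence, "Any remaining missing values which are not able to be adjudicated will be excluded from the analyses", but it follows text on adjudicating the primary endpoint and does not settle TMA.

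For a neighbouring exploratory endpoint, EBV-associated lymphoproliferative disorder, SAP 4.3.4 retains the protocol method: incidence is "described using the Aalen-Johansen estimator, treating death as the competing risk".

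**The concern.** The two documents prescribe different analyses of the same endpoint, and the SAP does not acknowledge the change. The SAP version is also incomplete. A patient who dies or is lost before 6 months without TMA could be put in *No* or in "Not Evaluable", and nothing in the plan decides which. Two analysts could report different TMA rates from the same data.

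TMA is worth estimating well here. The protocol's toxicity text (2.5.3) cites an "increase in TMA from 4.2% when patients were treated with tacrolimus or cyclosporine alone compared to 10.8% in patients treated with the tacrolimus/sirolimus combination" and calls the complication potentially serious. A between-arm test has little power for a difference of that size in this trial, so the estimate and its interval carry most of the information, and the interval is what the SAP shell leaves out.

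**Working it through.** The documents state no sample size, power or error rate for TMA, so there is no plan figure to reproduce.

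**Step 1. Which endpoints changed?** The protocol assigns cumulative incidence with Gray's test to six endpoints.

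| Endpoint | Protocol | SAP | Method kept? |
|---|---|---|---|
| Chronic GVHD | 5.2.5 item 4 | 4.2.4 | yes |
| Serious infection | 5.2.5 item 5 | 4.2.5 | yes |
| Non-relapse mortality | 5.2.5 item 10 | 4.2.10 | yes |
| Immune suppression discontinuation | 5.2.6 item 3 | 4.3.3 | yes |
| EBV lymphoproliferative disorder | 5.2.6 item 4 | 4.3.4 | yes |
| TMA | 5.2.6 item 8 | 4.3.8 | no |

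**Step 2. Inputs for size.**
- TMA rates of 10.8% and 4.2% (Protocol 2.5.3), assumed to be true 6-month incidences in the two arms.
- 60 analysed per arm (SAP 2.1).
- d, the proportion who die without TMA by 6 months. The documents do not give it. I take 5–25%, guided by the 6-month non-relapse mortality in Protocol 1.3 (under 10% for AA1, about 25% for AA2).
- Independent loss of 0–15% and constant hazards, both assumed.

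**Step 3. No losses, deaths counted as *No*.** Without censoring, the Aalen-Johansen increment at each TMA event is S(t−)/r = (r/n)/r = 1/n, where r is the number at risk. The estimate is therefore events/n, the simple proportion. A simulated 60-patient data set gave 11.67% both ways. Deaths cause no distortion here.

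**Step 4. No losses, deaths without TMA excluded.** The rate becomes c/(1−d), where c is the true incidence.

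| d | true 10.8% reads | true 4.2% reads |
|---|---|---|
| 5% | 0.108/0.95 = 11.4% | 0.042/0.95 = 4.4% |
| 10% | 0.108/0.90 = 12.0% | 0.042/0.90 = 4.7% |
| 20% | 0.108/0.80 = 13.5% | 0.042/0.80 = 5.3% |
| 25% | 0.108/0.75 = 14.4% | 0.042/0.75 = 5.6% |

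With unequal mortality (assumed), the true difference of 10.8 − 4.2 = 6.6 points becomes 14.4 − 4.7 = 9.7 points if d is 25% on sirolimus and 10% on prednisone. In the reverse case it is 12.0 − 5.6 = 6.4 points.

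**Step 5. Losses before 6 months.** Simulation of 1,000,000 patients, true incidence 10.8%, d = 10%:

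| Loss | lost = *No* | lost excluded | lost and deaths without TMA excluded |
|---|---|---|---|
| 5% | 10.6% | 11.1% | 12.3% |
| 10% | 10.3% | 11.3% | 12.7% |
| 15% | 10.1% | 11.6% | 13.0% |

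In the first two columns deaths without TMA stay in the denominator. Aalen-Johansen handles independent losses by censoring.

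**Step 6. TMA followed by death.** If patients with TMA who later die were also set aside, the error reverses. With half of TMA patients dying (assumed) and d = 10%, the rate is 0.108×0.5/(1 − 0.10 − 0.108×0.5) = 0.054/0.846 = 6.4%.

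**Step 7. Precision.** At 10.8% with n = 60, the standard error is √(0.108×0.892/60) = 4.0 points, so a Wald 95% interval is about ±7.9 points. Power for 4.2% vs 10.8% at two-sided 5%: the pooled standard error is √(2×0.075×0.925/60) = 0.0481 and the unpooled one √((0.108×0.892 + 0.042×0.958)/60) = 0.0477, so Φ((0.066 − 1.96×0.0481)/0.0477) is about 28%.

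**The case against.** A reader might infer that the third row of Exhibit 1501-20 removes early deaths and that the SAP therefore biases the TMA rate. The documents do not support that. SAP 4.3.8 speaks of a proportion of participants, and SAP 2.8.1 makes the population all randomized AA1/2 participants by intention to treat. Other shells do not use "Not Evaluable" to mean dead. Exhibit 1501-3 lists deaths in a separate row. Exhibits 1501-6 and 1501-12 count death as an event and still have a not-evaluable row. Keeping deaths without TMA as *No* is also the correct competing-risk treatment, as step 3 shows. These shells make exclusion less likely, but none of them states a rule for TMA.

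Other limits stand too. TMA is exploratory and is not one of the two monitored safety endpoints. Protocol Table 1 lists increased risk of CNI-induced HUS/TTP/TMA among rare toxicities (under 2%), which sits uneasily beside the 10.8%. Other SAP endpoints, such as CMV treatment by Day 56, are legitimately analysed as proportions. SAP section 5 calls the shells illustrative. With about 28% power, the choice of test changes little.

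What remains is an unexplained change of method, an unstated rule for deaths and losses, and a planned interval that has disappeared.

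**Conclusion.** The mismatch is real and confined to TMA among the protocol's six cumulative-incidence endpoints. Its numerical effect depends on a rule that the SAP leaves open. It is nil if deaths without TMA count as *No* and follow-up is complete. For an assumed true 10.8%, it is roughly 0.2 to 0.8 points in either direction for losses of 5–15% at d = 10%. It is upward by 1.2 points (d = 10%) to 3.6 points (d = 25%) if deaths without TMA are excluded. A change in the between-arm difference through unequal deaths needs both that exclusion and a mortality imbalance that the documents do not predict, so it should not be claimed as an expected bias.

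These shifts are smaller than the sampling error of about ±7.9 points with 60 patients. The figures assume that the cited TMA rates apply as 6-month incidences, together with constant hazards and independent loss. This is a minor point on an exploratory endpoint, worth correcting because the better method is already in the protocol.

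**What to change.** In SAP 4.3.8 and Exhibit 1501-20, restore the protocol analysis: Aalen-Johansen estimate by arm with death as the competing event, losses censored at last contact, Gray's test, and the 6-month estimate with 95% CI.

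The cost is SAP wording and one shell, since five other endpoints already need the same code. The condition is that TMA onset dates are available. The protocol's own analysis requires them, but the assessment schedule in Protocol Table 4.4 has no TMA row, and the documents do not show where the date is recorded. This should be checked first.

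If the dates cannot be obtained, keep the proportion, state the reason for the change, and add four rules: deaths without TMA stay in the denominator as *No*; TMA before death counts as *Yes*; "Not Evaluable" is limited to patients lost before 6 months without TMA; and the 95% CI is reported.

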#### **4.3.9 CMV reactivation**

The proportion of participants with previous CMV exposure (either donor or recipient was previously CMV+) requiring new systemic treatment for an increasing CMV PCR level per institutional practice (participants receiving only standard of care viral prophylaxis will not be included in this assessment) by Day 56 post-randomization will be compared between treatment groups using a Z-test for comparing binomial proportions (or Barnard's Exact Unconditional Test as appropriate).

#### **4.3.10 Patient-Reported Outcomes**

Patient-Reported Outcomes (PROs) assessed include the MDASI (MD Anderson Symptom Inventory), FACT-BMT, and MOS Short Form-36 (or PedsQL for pediatric participants) at enrollment and at Day 56, 6 months, and 12 months post-randomization. These will be scored per the recommendations of the developers. PROs at each time point will be summarized using simple descriptive statistics (mean, standard deviation, median, and range). PROs among survivors at each time point will be compared between treatment arms in an initial analysis using two sample t tests. The missing data pattern of the PRO measurements may be examined using graphical techniques and logistic regression models conditional on survival where, at each time point, estimates of the difference in PROs between the treatment groups conditional on survival would be obtained using inverse probability of censoring weighting with independent estimating equations to account for missing data.

#### **4.3.11 Secondary Analysis of AA3 Participants**

A secondary analysis will assess study outcomes for AA3 participants by treatment group (note that participants with missing biomarker results will be excluded). Due to the small number of AA3 participants expected, this analysis will be descriptive only as we are unlikely to have power to detect differences between the groups.

## **5. Template of Proposed Table/Figure/Listing (TFL) Shells**

Table/Figure/Listing titles and layout are for illustration purposes only, and may not be the final layout or wording chosen for publications or presentations. Actual format of the

tables and figures may differ and will be subject to change in the final analysis report and/or publication. See the Appendix of this SAP for the exhibit titles and shells.

## Appendix

### ***Exhibit 1501-1: Participant Disposition and Follow-Up***

A consort diagram will be provided showing the number of participants, study assignment, and compliance with each phase of the protocol as applicable. A table will be provided with descriptive statistics on length of follow-up by assigned treatment arm.

### ***Exhibit 1501-2: Participant Demographics and Baseline Characteristics***

Baseline characteristics and demographics will be described by frequencies and percentages for categorical covariates, and mean, standard deviation, median, and range for continuous covariates. The following covariates will be included:

- Treatment group assignment
- Gender
- Ethnicity
- Race
- Patient age
- Karnofsky performance score
- Primary Disease
- Disease Status
- Conditioning regimen
- Conditioning regimen intensity
- Donor type
- Graft source
- HLA match score
- GVHD Prophylaxis at Transplant
- Donor/Recipient CMV Status
- Acute GVHD grade at enrollment
- Acute GVHD organ staging at enrollment
- Topical steroid use at enrollment
- Ann Arbor biomarker status

Other baseline covariates will be summarized at the request of the investigators.

	Treatment Arm		
	Sirolimus (N=) N (%)	Prednisone (N=) N (%)	Total (N=) N (%)
Gender			
Female			
Male			
Ethnicity			
Hispanic or Latino			
Not Hispanic or Latino			
Unknown			

	Treatment Arm		
	Sirolimus (N=) N (%)	Prednisone (N=) N (%)	Total (N=) N (%)
Not Answered			
Race			
American Indian/Alaskan Native			
Asian			
Hawaiian/Pacific Islander			
Black or African American			
White			
More than One Race			
Other, Specify			
Unknown			
Not Answered			
Age, years			
Mean (Std Dev)			
Median (Range)			
Ann Arbor Biomarker Status			
1			
2			
3			
Missing			
Karnofsky Performance Score			
90 - 100			
Less than 90			
Primary Disease			
Acute Lymphoblastic Leukemia (ALL)			
Acute Myelogenous Leukemia (AML)			
Chronic Myelogenous Leukemia (CML)			
Other Leukemia			
Myelodysplastic/Myeloproliferative Disorders (MDS/MPN)			
Non-Hodgkin Lymphoma (NHL)			
Hodgkin Lymphoma			
Plasma Cell Disorder/Multiple Myeloma			
Inherited Abnormalities Erythrocyte Differentiation or Function			
Disease Status			
Complete remission (CR)			

	Treatment Arm		
	Sirolimus (N=) N (%)	Prednisone (N=) N (%)	Total (N=) N (%)
Partial remission (PR)			
Stable disease (SD)			
Conditioning Regimen			
ATG + FLUD + MEL			
BU + ATG + clofarabine			
BU + ATG + FLUD			
BU + ATG + FLUD + vorinostat			
BU + FLUD			
BU + FLUD + THIO			
CY + BU			
CY + BU + FLUD			
FLUD + MEL			
TBI +CY			
TBI + CY + FLUD			
TBI + FLUD			
Conditioning Regimen Intensity			
Myeloablative			
Non-myeloablative or Reduced Intensity			
Donor Type			
Related Donor			
Unrelated Donor			
Graft Source			
Bone Marrow			
Peripheral Blood			
Cord Blood			
HLA Match Score			
Bone marrow or peripheral blood 8/8			
Bone marrow or peripheral blood 7/8			
Bone marrow or peripheral blood <= 6/8			
Cord blood 6/6			
Cord blood 5/6			
Cord blood <= 4/6			
Missing			
GVHD Prophylaxis at Transplant			

	Treatment Arm		
	Sirolimus (N= N (%))	Prednisone (N= N (%))	Total (N= N (%))
Post-CY + Other(s)			
TAC + MMF +- Other(s) (except post-CY)			
TAC + MTX +- Other(s) (except MMF, post-CY)			
CSA + MMF +- Other(s) (except post-CY)			
CSA + MTX +- Other(s) (except MMF, post-CY)			
Donor/Recipient CMV Status			
Pos/Pos			
Pos/Neg			
Neg/Pos			
Neg/Neg			
Acute GVHD Grade at Enrollment			
0			
I			
II			
III			
IV			
Acute GVHD Skin Organ Stage at Enrollment			
0			
1			
2			
3			
4			
Acute GVHD Upper GI Organ Involvement at Enrollment			
Yes			
No			
Acute GVHD Lower GI Organ Stage at Enrollment			
0			
1			
2			
3			
4			
Acute GVHD Liver Organ Stage at Enrollment			
0			

	Treatment Arm		Total (N=) N (%)
	Sirolimus (N=) N (%)	Prednisone (N=) N (%)	
1			
2			
3			
4			
Topical Steroid Use at Enrollment			
Yes			
No			

 ATG = antithymocyte globulin, BU = Busulfan, FLUD = Fludarabine, CY = Cyclophosphamide, MEL = Melphalan, TBI = Total body irradiation, THIO = Intrathecal thiotepa

**Exhibit 1501-3: Complete Response / Partial Response at Day 28**

The primary endpoint is complete response/partial response (CR/PR) of acute GVHD to therapy at Day 28 post-randomization. Participants that have died prior to Day 28 or receive secondary therapy are treated as nonresponders in the analysis.

Acute GVHD Response at Day 28 by Treatment Group		
	Sirolimus (N=) N (%)	Prednisone (N=) N (%)
Complete Response (CR)	XX (XX.X%)	XX (XX.X%)
Partial Response (PR)	XX (XX.X%)	XX (XX.X%)
Mixed Response (MR)	XX (XX.X%)	XX (XX.X%)
No Response (NR)	XX (XX.X%)	XX (XX.X%)
Progression	XX (XX.X%)	XX (XX.X%)
Dead	XX (XX.X%)	XX (XX.X%)
Not Evaluable	XX	XX

Day 28 CR/PR Rates				
	N Evaluable	Estimate	Standard Error	90% CI
Sirolimus	XX	XX.X%	XX.X%	(XX.X%, XX.X%)
Prednisone	XX	XX.X%	XX.X%	(XX.X%, XX.X%)
Difference (Sirolimus – Prednisone)	XX	XX.X%	XX.X%	(XX.X%, XX.X%)

*Clarify the population for the endpoint (n=?). If n is not the same as the primary endpoint, explain why (e.g. patient not evaluable, missing data, etc.) Give details of not evaluable if the definition is not pre-specified in the protocol.*

**Exhibit 1501-4: Complete Response / Partial Response and Steroid Dose 0.25/mg/kg/day or Less at Day 28**

This is a refined endpoint of CR/PR and the use of a prednisone equivalent steroid dose of 0.25 mg/kg/day or less. Methylprednisone is considered to be 1.25 times as potent as prednisone, while prednisolone is dose-equivalent to prednisone. Note that use of prednisone below the threshold on the sirolimus arm is not considered a failure for this endpoint. Participants that have died or received secondary therapy prior to Day 28 are treated as nonresponders in the analysis.

Day 28 CR/PR and Steroid Dose 0.25/mg/kg/day or Less by Treatment Group			
	Sirolimus (N=) N (%)	Prednisone (N=) N (%)	P-value*
Yes	XX (XX.X%)	XX (XX.X%)	X.XXX
No	XX (XX.X%)	XX (XX.X%)	
Not Evaluable	XX	XX	

\* Clarify test used (Z test of binomial proportions or Barnard's Exact)

Rates of Day 28 CR/PR with Steroid Dose 0.25/mg/kg/day or Less				
	N Evaluable	Estimate	Standard Error	95% CI
Sirolimus	XX	XX.X%	XX.X%	(XX.X%, XX.X%)
Prednisone	XX	XX.X%	XX.X%	(XX.X%, XX.X%)

Clarify the population for the endpoint (n=?). If n is not the same as the primary endpoint, explain why (e.g. patient not evaluable, missing data, etc.) Give details of not evaluable if the definition is not pre-specified in the protocol.

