#### 2.5.7. Management of study therapy after GVHD Progression or Non-response:

The following guidelines describe intended management of initial randomized therapy and thresholds for starting secondary therapy:

1. Initial randomized therapy should be given for at least 4 days before considering initiation of secondary therapy. As progressive manifestations of GVHD (new organ involvement or increased organ specific symptoms sufficient to increase the organ stage by one or more) can be ultimately stabilized and controlled in this initial therapy timeframe, secondary therapy should only be considered if GVHD continues to progress after this period.

2. If no response (no improvement in any affected organ) is observed after 7-10 days of initial randomized therapy, secondary therapy can be considered.

# CHAPTER 3

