# **3.1.1.** Response Definitions

Scoring of CR, PR, MR, NR and progression are in comparison to the participant's acute GVHD status (score) on the day of randomization.

**CR is defined as a score of 0 for the GVHD grading in all evaluable organs.** For example, for a response to be scored as CR at Day 56 or later, the participant must still be in CR on that day and have had no intervening additional therapy for an earlier progression, PR or NR.

**Partial response (PR) is defined as improvement in one or more organs involved with GVHD symptoms without progression in others.** For example, for a response to be scored as PR at Day 28 or later, the participant must still be in PR on that day and have had no intervening additional therapy for an earlier progression, PR or no response (NR).

Mixed response (MR) is defined as improvement in one or more organs with deterioration in another organ manifesting symptoms of GVHD or development of symptoms of GVHD in a new organ.

Progression is defined as deterioration in at least one organ without any improvement in others.

No response (NR) is defined as absence of any improvement or progression as defined. Patients receiving secondary therapy (including need to re-escalate steroid dose to  $\geq 2.5$  mg/kg/day of prednisone [or methylprednisolone equivalent of 2 mg/kg/day]) will be classified as non-responders. Patients who are assigned to the sirolimus arm who require initiation of systemic corticosteroids for the treatment of acute GVHD will be considered as non-responders for purposes of primary endpoint assessment.

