# **3.2.** Secondary Endpoints

#### 3.2.1. Proportion of Patients with CR/PR and Steroid Dose 0.25 mg/kg or less

The proportion of patients with an acute GVHD response on Day 28 (CR or PR) and who are on a prednisone (or prednisone dose-equivalent corticosteroid) dose of 0.25mg/kg/day or less. Note

that use of prednisone below the threshold on the sirolimus arm will not be considered a failure for this endpoint.

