#### Post-Randomization

The following post-randomization assessments are required of all patients, regardless of therapy received.

- 1. Karnofsky or Lansky performance status at Days 56, 90, 180 and 365
- 2. Complete acute GVHD staging and grading information including assessments of rash, diarrhea, nausea/vomiting, weight and liver function tests weekly through Day 56; Day 90, 6 and 12 months
- 3. Chronic GVHD evaluation (if present) Day 28, 56, 90, and 6 and 12 months
- 4. CBC with differential, chemistry (including liver function tests) weekly through Day 56; Day 90, 6, and 12 months
- 5. Fasting lipid profile at Day 28, 56, and 6 months
- 6. Toxicity evaluation weekly through Day 56; Day 90, 6 months and 12 months
- 7. Recording of all systemic immune suppression, including steroid dose and drug levels (as appropriate for sirolimus, cyclosporine, tacrolimus) weekly through Day 56, Day 90, 6, and 12 months. Second-line immune suppressive therapy (therapy beyond initial

randomized therapy of either sirolimus or prednisone) should be recorded at each of these time points.

- 8. Use of topical (skin, GI) steroid agents weekly through Day 56; Day 90, 6 and 12 months.
- 9. Data on systemic infections, and EBV PTLD (or EBV requiring therapy), recorded as per the BMT CTN (Technical) MOP through 12 months.
- 10. EBV & CMV monitoring as per institutional practice.
- 11. Myopathy assessments at Day 56 and 6 months.\*
  - a. Hip Flexor and Quadriceps Strength via handheld dynamometer
  - b. Two Minute Walk Test
  - c. 5-time Sit-to-Stand
  - d. Adult Myopathy Assessment Tool (AMAT)
- 12. Patient reported outcomes (M.D. Anderson Symptom Inventory, FACT-BMT, SF-36, or PedsQL (Pediatrics)) at Day 56, 6 months and 1 year.\* Only English speaking adult and pediatric patients, and Spanish speaking adult patients are eligible to participate in the Health Quality of Life (HQL) component of this trial. Patients >18 years will complete the FACT-BMT, MOS SF-36 and MDASI instruments. Patients ≥ 8 years through 18 years will complete the PedsQLTM Stem Cell Transplant Module.
- 13. OPTIONAL 30-40 mL blood samples for research laboratory studies at Day 7, 28, and 56 (see Appendix B).\* Patients with weight <13 kg will have ≤3 mL/kg collected at each individual time point.

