# 5.2.2. Guidelines for Safety Monitoring

Monitoring of two key safety endpoints will be conducted monthly, and if rates significantly exceed pre-set thresholds, the NHLBI will be notified in order that the DSMB can be advised. Policies and composition of the DSMB are described in the BMT CTN's Manual of Procedures. The stopping guidelines serve as trigger for consultation with the DSMB for additional review. The key safety endpoints for this study are: 1) failure of sirolimus therapy with a failure for the stopping rule defined as the addition of a systemic immune suppressive therapy beyond prednisone among those patients originally treated with sirolimus and 2) overall mortality. Both of these endpoints will be monitored among AA1/2 patients only; failure of sirolimus therapy will be monitored in the sirolimus arm only.

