### **4.2.1 Proportion of Participants with CR/PR and Steroid Dose 0.25 mg/kg/day or Less**

This is a refined endpoint of CR/PR and the use of a prednisone equivalent steroid dose of 0.25 mg/kg/day or less. The rates of CR/PR and steroid dose 0.25 mg/kg/day or less will be estimated within each arm and compared between arms using the Z test for binomial proportions (or Barnard's Exact Unconditional Test as appropriate). Methylprednisone is considered to be 1.25 times as potent as prednisone, while prednisolone is dose-equivalent to prednisone. Note that use of prednisone below the threshold on the sirolimus arm will not be considered a failure for this endpoint. Participants that have died prior to Day 28 will be treated as nonresponders in the analysis.

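### Does the secondary-therapy sentence in SAP Exhibit 1501-4 cancel the prednisone exemption on the sirolimus arm?

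*SAP*

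**What the plan says.** Protocol 3.2.1 defines the endpoint by Day 28 response and the steroid dose the patient is on, and adds that "use of prednisone below the threshold on the sirolimus arm will not be considered a failure" for it. SAP 4.2.1 repeats the exemption and names one automatic nonresponse: "Participants that have died prior to Day 28 will be treated as nonresponders in the analysis". Exhibit 1501-4 repeats the exemption too, and its next sentence reads "Participants that have died or received secondary therapy prior to Day 28 are treated as nonresponders in the analysis".

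The response definitions (Protocol 3.1.1, repeated in SAP 4.1) contain two separate rules. The first begins "Patients receiving secondary therapy (including need to re-escalate steroid dose to" and makes such patients non-responders. The second covers sirolimus patients who need systemic corticosteroids for acute GVHD; they "will be considered as non-responders for purposes of primary endpoint assessment".

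Usage elsewhere varies. Protocol 2.5.7 says "Initial randomized therapy should be given for at least 4 days before considering initiation of secondary therapy". The post-randomization list in Protocol 4.4 says that second-line therapy beyond the initial "randomized therapy of either sirolimus or prednisone) should be recorded at each of these time points". The safety rule in Protocol 5.2.2 counts as sirolimus failure only the "addition of a systemic immune suppressive therapy beyond prednisone among those patients originally treated with sirolimus".

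**The concern.** Two adjacent sentences in the exhibit seem to pull apart: one exempts prednisone on sirolimus, the next fails anyone given secondary therapy. If that term means whatever follows the randomized drug, as Protocol 2.5.7 and 4.4 can be read, prednisone added to sirolimus is caught. SAP 4.2.1 mentions only death, so an analyst working from the text and one working from the exhibit might report different sirolimus rates from the same data.

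The affected patients would not be rare. In the background cohort (Protocol 1.5), 16 of 32 sirolimus patients started steroids, at a median of 0.5 mg/kg. This is also the endpoint with a stated power, and it is tested at 5%. Because the reading of steroid start matters only on sirolimus, any reclassification moves the treatment difference directly.

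**Working it through.** **1. The plan's own power figure.** Inputs from Protocol 5.1.5 and SAP 2.1: 60 per arm, 30% prednisone, 55% sirolimus, two-sided 5%.
- Normal approximation: the pooled rate is (0.30 + 0.55)/2 = 0.425. Null SE = √(2 × 0.425 × 0.575/60) = 0.0903. Alternative SE = √((0.30 × 0.70 + 0.55 × 0.45)/60) = 0.0873. Power = Φ((0.25 − 1.96 × 0.0903)/0.0873) = 79.9%.
- Full enumeration of the pooled Z test over two binomials of 60 gives 80.6%, the stated figure.

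**2. How far the two readings can differ.** Inputs from Protocol 5.1.5: 27 standard-risk sirolimus patients, CR/PR 88.9% overall and 55.6% if any prednisone is failure.
- 0.889 × 27 = 24 responders; 0.556 × 27 = 15 without prednisone; 24 − 15 = 9 responders had prednisone.
- Their Day 28 doses are not given, so between 0 and 9 would meet the dose limit. That is 0 to 33.3 points, or 0 to 9 × 60/27 = 20 patients in an arm of 60.
- Enumerated power against 30% is 82.3% at 15/27 and above 99.9% at 24/27. Lenient scoring can only raise the sirolimus rate, so 80.6% is not overstated by it.

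**3. What the difference does to the test.** Pooled Z test, 60 per arm, illustrative counts:

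| Prednisone | Sirolimus | p |
|---|---|---|
| 18 | 33 | 0.006 |
| 18 | 28 | 0.060 |
| 18 | 29 | 0.040 |
| 24 | 33 | 0.10 |
| 24 | 35 | 0.045 |

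At the planned rates (18 against 33) significance does not depend on the reading. The other rows assume a lower sirolimus count or a higher prednisone rate than planned.

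**4. Which reading the text supports.**
- *Separate sentences.* In Protocol 3.1.1 and SAP 4.1, steroid start on sirolimus has its own sentence, limited to the primary endpoint. If it were already secondary therapy, that sentence would be redundant. Treatment failure (Protocol 3.2.3, SAP 4.2.3) also lists steroid start separately from additional therapy.
- *The exemption needs work to do.* If any steroid start on sirolimus failed, the exemption would cover little beyond steroids given for reasons other than GVHD, such as the adrenal replacement doses allowed in Protocol 2.4.2. The sirolimus rate would be almost the primary-endpoint rate again.
- *Dose is judged on Day 28.* Every prednisone patient starts at 2 mg/kg/day, 2/0.25 = 8 times the threshold. If an earlier dose above the threshold disqualified a patient, no prednisone patient treated as assigned could succeed. The criterion is therefore the dose on Day 28, and the same criterion fits sirolimus.
- *The exhibit and SAP 4.2.1 are not two rules.* The endpoint is built on CR/PR, and SAP 4.1 already makes secondary therapy a non-response. The exhibit restates an inherited rule that 4.2.1 leaves implicit.

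**The case for a change.** The strongest case for changing the text is that the intended reading is inferred. No sentence says that secondary therapy excludes prednisone for this endpoint. Exhibit 1501-3 summarises primary non-response as death or secondary therapy, and there that phrase is the only one that can carry the steroid-start rule; the next exhibit uses the same phrase. The planned 55% lies close to the 55.6% obtained by counting any prednisone as failure, which could suggest strict scoring was in mind. The trial is open label, so scoring is best fixed before the data are seen. SAP 2.2 describes committee adjudication of the primary endpoint only, and the charter mentioned in SAP 2.6 is not among the documents.

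Part of this stands. The term is undefined, and a sirolimus patient above 0.25 mg/kg/day earlier but at or below it on Day 28 is not expressly classified. At least 8 of the 16 background patients who started steroids did so at 0.5 mg/kg or more (the median of 16 values is 0.5), so the case can arise.

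The rest carries less weight. Protocol 2.5.7 is management guidance and the list in Protocol 4.4 is a recording instruction; neither scores this endpoint. The safety rule sets prednisone apart. No text links 55% to 55.6%; if the strict figure was used, planning sits at the conservative end. Power at prednisone rates above 30% is a separate matter. The documents already warn that the 22.1% background rate may be too low, plan at the upper confidence limit, and tie 80.6% to 30% against 55%.

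**Conclusion.** No change to the plan follows. The apparent contradiction comes from one undefined term in a table shell, and SAP section 5 says shell wording is not final. Three places state the exemption, the response definitions confine the steroid-start rule to the primary endpoint, and the broad reading would leave the exemption nearly empty. An analyst would apply the Day 28 dose to sirolimus patients who started prednisone, and count death, other added systemic agents and the defined steroid re-escalation as non-response. Weekly steroid dose and second-line therapy are already recorded, so nothing needed for that scoring is missing.

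The number of patients who turn on the reading cannot be derived. The bound of 0 to 9 of 27, or 0 to about 20 of 60, assumes the background cohort carries over and lets every prednisone-treated responder fall on either side of the dose limit. At the planned rates the test is significant either way (p = 0.006 at 18 against 33), the stated power is correct, and no success criterion for the trial rests on this endpoint. The conclusion rests on inferred intent, but the inference is well supported by the plan's own wording.
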